### Protocol Phase 1 – Temporary Trial Neurostimulation

Following consent and entry into the prospective trial, baseline assessments will be taken. Subjects will then have the quadrapolar leads epidurally placed using a percutaneous approach and steered towards the appropriate intraspinal location (see *Physician Implant Manual* for detailed information regarding the procedure).

### Protocol Phase 2 – Implantable Stimulation

If a subject obtains sufficient pain relief either overall or in their primary area of pain during the TNS procedure or during the course of the trial phase of the study, the subject will be eligible to continue onto the Implantable Phase of the study. All eligible subjects willing to continue will undergo another surgical procedure to fully-implant the neurostimulator (see *Physician Implant Manual* for detailed information regarding the procedure).

**Follow-up**

Subjects will be followed for 24 months following implant, returning to the clinic at regular follow-up time points in line with standard clinical care (1 week, 4 weeks, 3 months, 6 months, 12 months and 24 months). Subjects have the option to return to the clinic at unscheduled times to have the device reprogrammed as needed. This can be captured as an interim visit. The site can contact the patients by phone at 8 weeks, 9 months and 18 months (optional).

**4. STUDY POPULATION****4.1 Population**

████████ male and female subjects (minimum age 18 years old) suffering from chronic intractable pain for a minimum of 6 months who are routinely scheduled for DRG stimulation will be recruited █████ for inclusion in the trial.

Subjects must meet all of the inclusion and none of the exclusion criteria to be enrolled in the prospective trial. Subjects will read and sign an informed consent prior to undergoing any data collection or trial treatment. Subjects will be recruited from the sites existing patient population and through new patient contacts as normally progresses in standard clinical practice.

**4.2 Inclusion criteria**

- 1) Subject is at least 18 years old
- 2) Subject is able and willing to comply with the follow-up schedule and protocol
- 3) Chronic, intractable pain for at least 6 months
- 4) Failed conservative treatments for chronic pain including but not limited to pharmacological therapy, physical therapy and interventional pain procedures for chronic pain
- 5) Average baseline pain rating of 60 mm on the VAS in the primary region of pain
- 6) In the opinion of the Investigator, the subject is psychologically appropriate for the implantation for an active implantable medical device
- 7) Subject is able to provide written informed consent

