## 3. STUDY DESIGN

This study is a prospective, post market, single-arm, multi centre trial designed to assess the clinical effects of the commercially available Axium® Neurostimulator System in the management of chronic intractable pain. Subjects that are routinely scheduled to receive DRG stimulation will be asked to participate in this trial. They will be screened based upon the inclusion and exclusion criterion, consented with an REC approved Patient Informed Consent Form, and enrolled into the trial. Subjects will then be assessed for baseline measurements.

Patients that are not willing to participate in the trial or that do not fulfill the inclusion criteria, but are, nevertheless, considered to be suitable for neurostimulation will be treated as such under standard of clinical care at the pain clinic.

Subjects will “trial” the therapy with an external Trial NeuroStimulator (TNS), for a maximum of 30 days (Phase 1) depending on standard hospital practice. If subjects obtain sufficient pain relief either overall or in their primary area of pain being treated, they will be eligible to proceed with the second phase of the therapy. If the eligible subjects agree to move forward into Phase 2, they will receive the fully Implantable NeuroStimulator (INS). Subjects will be seen for follow-up at 1 week, 4 weeks, 3 months, 6 months, 12 months and 24 months following implantation (Figure 1). The site can contact the subjects by phone for a follow-up at 8 weeks, 9 months and 18 months (optional).

**Figure 1.** Basic design and follow-up schedule for subjects enrolled into the PREDICT trial. Subjects consented and enrolled will undergo a two-phase process for advancement through the trial. Subjects that do not obtain at sufficient pain relief during Phase 1 will be considered screen failures. A detailed follow-up scheduled can be found in Appendix A.

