#### 4.4 Sample size calculation

### 5. TREATMENT OF SUBJECTS

#### 5.1 Treatment

The *Physician Implant Manual* provides a detailed description of the implant and surgical technique. Following informed consent and baseline measurements, subjects will begin phase one of a two-phase treatment process. Phase 1 is the Trial Phase and consists of percutaneously implanting neurostimulator leads into the epidural space and attaching them to an external neurostimulator. This system is then “trialed” during the TNS procedure and if needed up to a maximum of 30 days. If the subject experiences sufficient pain relief overall or in their primary area of pain being treated during the trial phase, they will progress to Phase 2, the implantation phase. In this phase, the implanted leads will be connected to a fully implantable neurostimulator. The entire system is then implanted under the skin for the

duration of device use. As a result of the device design, the therapy is fully reversible and can be removed through a similar minor procedure.

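### Does the 60 mm VAS inclusion criterion, written without a direction and resting on a baseline that section 3 takes after enrolment, need to be changed?

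*Protocol*

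**What the plan says.** Section 4.2, criterion 5, requires "Average baseline pain rating of 60 mm on the VAS in the primary region of pain". Criteria 1 (age) and 3 (pain duration) in the same list are explicit minimums. Criterion 5 is a complete sentence, so no words have been lost to redaction.

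On enrolment, section 4.1 states: "Subjects must meet all of the inclusion and none of the exclusion criteria to be enrolled in the prospective trial". Section 7.3 repeats the rule. Section 4.1 also states: "Subjects will read and sign an informed consent prior to undergoing any data collection or trial treatment".

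On sequence, section 3 says of candidates: "They will be screened based upon the inclusion and exclusion criterion, consented with an REC approved Patient Informed Consent Form". It continues: "enrolled into the trial. Subjects will then be assessed for baseline measurements". The Phase 1 text in section 3 agrees: "Following consent and entry into the prospective trial, baseline assessments will be taken". Section 5.1 puts it differently: "Following informed consent and baseline measurements, subjects will begin phase one of a two-phase treatment process". Section 7.3 places the baseline assessment after screening and consent and before lead implantation. It defines the baseline VAS as the mean of a 4-day diary kept before the trial procedure, and it asks for a pregnancy test before entry.

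On people who do not continue, section 3 provides that patients who miss the inclusion criteria but are suitable for neurostimulation are treated under usual care at the pain clinic. The Figure 1 legend adds: "Subjects that do not obtain at sufficient pain relief during Phase 1 will be considered screen failures". Section 7.4 lets the investigator withdraw a subject on urgent medical grounds, and section 7.5 says withdrawn subjects are not replaced.

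**The concern.** Criterion 5 is the only numeric severity threshold for entry, and it has no inequality. Taken literally it admits only a diary mean of exactly 60 mm. Nothing else in the visible protocol supplies the direction, since the summary and section 4.1 give only age and pain duration.

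The order of events looks circular. A subject must satisfy criterion 5 to be enrolled, criterion 5 needs the baseline average, no data may be collected before consent, and section 3 takes baseline after enrolment. On that order the value that decides enrolment does not yet exist when enrolment happens.

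At stake would be the definition of the enrolled population. Two sites could record the same patient, one who consents and then has a diary mean that misses the threshold, as enrolled or as never enrolled. The enrolled count, capped at 125 in the summary, and any rate calculated on it could then depend on site practice.

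**Working it through.** The protocol attaches no calculation to this criterion, so the check compares its sections.

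**Direction.** There are three possible readings of 60 mm.

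- *Exactly 60 mm.* Almost nobody would qualify on a diary mean, so this cannot be meant.
- *A ceiling.* This would exclude the more severe pain from a trial in chronic intractable pain after failed conservative treatment (criteria 3 and 4).
- *A floor.* This matches the form of criteria 1 and 3. It also fits the primary objective in section 2, which counts subjects with at least a 50% reduction: from a baseline of 60 mm that requires a fall of 0.50 × 60 = 30 mm, whereas low baselines would make the responder definition nearly empty.

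Only the floor is workable.

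**Order.** The sequences, side by side:

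| Source | Sequence |
|---|---|
| Section 3, main text | screening, consent, enrolment, baseline |
| Section 3, Phase 1 | consent and entry, baseline, lead placement |
| Section 4.1 | consent before any data; all criteria before enrolment |
| Section 5.1 | consent, baseline, Phase 1 |
| Section 7.3 | screening, consent, baseline diary, lead implantation; pregnancy test before entry |

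Every row is compatible with consent coming before the diary, and every row that mentions the leads puts baseline before them. The rows disagree only on where the words for enrolment and entry fall. The working order of consent, diary, check of criterion 5, then lead placement satisfies sections 4.1, 5.1 and 7.3 in full. It departs from section 3 only in the point at which a person is called enrolled.

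**A patient who misses the threshold.**

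1. Sections 4.1 and 7.3 say that such a patient is not enrolled.
2. Section 3 says that such a patient, if suitable for neurostimulation, receives usual care.
3. Section 7.4 covers a subject who chooses to leave or an investigator who withdraws a subject on urgent medical grounds. A missed VAS threshold is neither, so the no-replacement rule in section 7.5 is not triggered.
4. The screen failures of the Figure 1 legend are a different group: they have had leads placed and did not obtain enough relief.

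**Effect on results.** A patient stopped at the diary does not start Phase 1 in the trial and so has no in-trial VAS after implantation. The mean reduction among implanted subjects, and the share of them with at least a 50% reduction, are the same whichever label the patient carries. Only a rate whose denominator is everyone ever called enrolled could shift.

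**The case for a change.** The strongest reply is that eligibility wording and the point of enrolment belong in the protocol and are not details for an analysis plan. The repair would be a few words, and leaving it undone lets sites label the same person differently. That is fair as a comment on drafting. The missing inequality and the conflict between section 3 and sections 4.1 and 7.3 are genuine, and section 3's usual-care paragraph does not say how to log someone who was counted as enrolled too early.

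A second argument is that many referrals may score below 60 mm, so the count could move a good deal. The protocol gives no score distribution, and section 10.2 says candidates come from patients whom the investigator has already chosen for this therapy. Any share would have to be assumed, and assuming an unscreened referral population would be the wrong starting point.

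A third is that selecting on the same diary that serves as the analysis baseline builds in some regression to the mean, which favours the device in a single-arm trial. That would follow from any severity threshold applied to the baseline score. Writing the inequality or moving the word for enrolment would not alter it. Whether the diary is the analysis baseline also cannot be seen, because section 9 is redacted. This argument does not bear on the wording or the order.

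**Conclusion.** No change to the plan follows. The missing direction is a clerical slip with one credible reading. The order conflict concerns when the word for enrolment applies, and sites can apply criterion 5 after consent and before lead placement under sections 5.1 and 7.3. The remaining gap is a bookkeeping label for anyone counted as enrolled before the diary mean was known, which an analyst can handle by reporting consented, Phase 1 and implanted numbers separately. No effect on a visible estimate or conclusion can be shown, and the documents do not allow the number of people affected to be estimated.

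This rests on three assumptions: sites read 60 mm as a minimum; they check the diary mean before the trial procedure; and Appendix A, which is not shown, does not contradict that order. A separate screening VAS in Appendix A would weaken the concern further.

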#### 4.3 Exclusion criteria

- 1) Female subject of childbearing potential is pregnant/nursing, plans to become pregnant or is unwilling to use approved birth control
- 2) Escalating or changing pain condition within the past month as evidenced by investigator examination
- 3) Subject has had corticosteroid therapy at an intended site of stimulation within the past 30 days
- 4) Subject has had radiofrequency treatment of an intended target DRG within the past 3 months
- 5) Subject currently has an active implantable device including ICD, pacemaker, spinal cord stimulator or intrathecal drug pump
- 6) Subject is unable to operate the device
- 7) Subjects currently has an active infection
- 8) Subject has, in the opinion of the Investigator, a medical comorbidity that contraindicates placement of an active medical device
- 9) Subject has participated in another clinical trial within 30 days
- 10) Subject has a coagulation disorder or uses anticoagulants that, in the opinion of the investigator, precludes participation
- 11) Subject has been diagnosed with cancer in the past 2 years

#### 4.4 Sample size calculation

### 5. TREATMENT OF SUBJECTS

#### 5.1 Treatment

The *Physician Implant Manual* provides a detailed description of the implant and surgical technique. Following informed consent and baseline measurements, subjects will begin phase one of a two-phase treatment process. Phase 1 is the Trial Phase and consists of percutaneously implanting neurostimulator leads into the epidural space and attaching them to an external neurostimulator. This system is then “trialed” during the TNS procedure and if needed up to a maximum of 30 days. If the subject experiences sufficient pain relief overall or in their primary area of pain being treated during the trial phase, they will progress to Phase 2, the implantation phase. In this phase, the implanted leads will be connected to a fully implantable neurostimulator. The entire system is then implanted under the skin for the

duration of device use. As a result of the device design, the therapy is fully reversible and can be removed through a similar minor procedure.

### **5.2 Use of co-intervention**

Subjects will be allowed to continue using medication for the treatment of their pain condition. The prescription of medication for pain will be dictated by the Principle Investigators and/or sub-investigator as per standard of care.

## 6. DESCRIPTION OF THE DEVICE

### 6.1 Name and description of Axium® Neurostimulator System

On 16 November 2011, BSI granted Spinal Modulation, Inc. CE mark for the Axium® Neurostimulator System for the Management of Chronic Intractable Pain (CE 567069). The system has been registered with the CIBG in the Netherlands on 24 November 2011.

The Spinal Modulation Axium® Neurostimulator System consists of the following components:

- Trial NeuroStimulator (TNS)
- Implantable NeuroStimulator (INS)
- Trial Lead Kit
- Implant Lead Kit
- Connector Cable Kit
- Tunnelling Tool Kit
- Clinical Programmer
- Patient Programmer
- Auxiliary Magnet Kit
- Programmer Charger Kit
- Programmer Carrying case
- Lead Accessories Kit
- 22 cm Small Curve Delivery Sheath Kit
- 22 cm Big Curve Delivery Sheath Kit
- Lead Extension Kit

A detailed description of the components can be found in the physician implant manual.

Briefly, the Axium® Neurostimulator System is a fully implantable medical device designed to aid in the management of intractable chronic pain. The device, which is surgically placed in a similar fashion to other approved spinal cord stimulator systems, produces controlled electrical stimulation to spinal neural tissue. A minimally invasive procedure, similar to that used by other approved spinal cord stimulator systems is used to place the device in the body. Also similar to approved spinal cord stimulator systems, individuals first undergo a trial phase in which they can test the effects of the stimulation. If they wish to continue with the therapy they will receive a fully implantable system. The implantable system is reversible in that it can be explanted at any time.

## 6.2 Summary of known and potential risks and benefits

A summary of the known and potential risks and benefits can be found in the accompanying manuals that are included in the package of the components. The general risks associated with the Axium® Neurostimulator System are similar to those associated with other currently approved Spinal Cord Stimulator systems. Possible risks to the subjects include both device and procedural based risks. The most common side effects and risks are:

- Pain (where the needle is to be inserted)
- Pain caused by understimulation due to lead migration
- Pain over the implantable neurostimulator site (only applicable in Phase 2)
- Escalating pain
- Bleeding (where the needle has been inserted)
- Headache
- Infection
- Localized collection of serous (clear) fluid at injection site
- Discomfort during the treatment
- Allergic or rejection response to implant materials
- Constant pain at the lead site
- Stimulation of the chest wall
- Lead migration (movement) and/or local skin breakage
- Weakness
- Clumsiness
- Numbness
- Temporary muscle activation

Very rare risks and side effects include:

- Cerebral Spinal Fluid (CSF) leakage
- Tissue damage
- Nerve damage
- Spinal cord compression
- Paralysis
- Hematoma
- Seroma
- Sensory loss
- Skin erosion around the INS or leads
- Battery failure and/or battery leakage
- Lead breakage requiring replacement of the lead
- Hardware malfunction requiring replacement of the neurostimulator
- Pain from a non-injurious stimulus to the skin (allodynia)
- An exaggerated sense of pain (hyperesthesia)

### 6.3 Device utilization

A detailed description of device utilization can be found in the Physician Implant Manual. All investigators involved in the study have been trained on the use of the Axium® Neurostimulator System.

## 6.4 Devices

The devices that will be used in the prospective trial have CE mark, are commercially available products and will be bought and paid for according to the standard hospital system. A label of the products used will be added to the patient files to document and identify the devices.

## 7. METHODS

## 7.1 Assessments

During the scheduled follow-ups the following assessments will be performed. Table 1 in appendix A gives a detailed description of the assessments per follow-up.

## 7.2 Randomisation, blinding and treatment allocation

As this is a single-arm study, no randomisation or blinding will occur.

### 7.3 Study procedures

1.15 Study procedures  
During the prospective trial, data will be collected on Case Report Forms (CRFs). A copy of the CRFs will be provided for review.

*Subject Screening and baseline*

Subjects presenting with chronic pain for at least 6 months will be screened for possible entry into the prospective trial. Subjects will be screened according to the Inclusion/Exclusion criteria and only subjects meeting all Inclusion criteria and none of the Exclusion criteria will be enrolled. The prospective trial will be explained to all subjects and subjects will provide informed consent with an REC-approved Informed Consent Form prior to any data collection. Subjects will be allowed to discuss their participation in the trial with the study physician, clinical staff, family, friends and personal or external physician.

Following subject screening and acquisition of Informed Consent, subjects will undergo a baseline assessment to collect clinical data prior to lead implantation and stimulation. Baseline pain scores (VAS) will be evaluated using the average score from a 4 day pain diary completed by subjects before their trial procedure. Women of child bearing potential will take an HCG-based pregnancy test to confirm that they are not pregnant prior to entry into the trial.

*Trial Stimulation Lead Implant Procedure*

Following collection of baseline measurements, subjects will begin Phase 1 of the two-step treatment process. Phase 1 is the Trial Phase and consists of percutaneously implanting quadrapolar neurostimulator leads into the epidural space. The techniques used in implanting the Spinal Modulation Neurostimulator System are consistent with standard of care practices used by other approved spinal cord stimulator systems. The *Physician Implant Manual* provides a detailed description of the implant and surgical technique. Perioperative programming will be performed to verify proper lead placement.

*End of Trial Phase*

At the end of the Trial Phase, pain relief will be assessed to determine whether a subject should receive an INS implant. This may be done in the theatre during the TNS procedure or after an extended trial period of no more than 30 days based upon the type of pain, the location of the pain, and the standard procedures at the hospital.

*INS Implant Procedure*

Eligible subjects willing to continue with the implant will undergo surgery to insert the fully implantable neurostimulator (INS). If the epidural leads were removed during the trial period, new leads will also be implanted at this time (see *Physician Implant Manual* for detailed information regarding the procedure). Each subject will receive a hand-held Patient Programmer that can be used to adjust stimulation amplitude as needed throughout the study duration.

Post-implant programming to adjust stimulation settings will occur either immediately after the surgery or the day following implantation.

*Regular Follow-ups*

Subjects will be followed according to the follow-up schedule for 24-months following implant at regular intervals according to standard clinical practice: 1-week ( $\pm 5$  days), 4 weeks ( $\pm 1$  week), 3 month ( $\pm 2$  weeks), 6 month ( $\pm 2$  weeks), 12 months ( $\pm 2$  weeks) and 24 months ( $\pm 2$  weeks). The given time-windows are advisable and therefore visits outside the time windows will not be seen as a protocol deviation. If desired, the Investigators may call the subjects for evaluation at 8-weeks, 9-months and 18 months post-implant.

Prior to completing the required assessments, the subject will have his/her stimulator reprogrammed if needed.

*24-month follow-up (Study Exit)*

The study will end 24 months following INS implantation. At this visit, the regular follow-up assessments as outlined in appendix A will be acquired and a trial exit form will be completed. Following completion of the study, subjects will continue to use the Axium® Neurostimulator System. They will be monitored by their physician as needed in accordance with standard clinical practice.

*Interim Programming/Revision/Replacement/Explant (if necessary)*

During the course of the trial, subjects will have the option to return to the study site at any time to have their neurostimulator re-programmed to achieve maximal benefit. If any part of the Axium® Neurostimulator System becomes dysfunctional or requires adjustment following implantation, it is up to the investigator to perform an interim visit. In appendix A, the assessments are listed for an interim visit and a revision (if applicable).

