## 2. OBJECTIVES

The objective for this prospective, multi centre DRG stimulation trial is to assess the performance of the commercially available CE marked Axium® Neurostimulator System in the management of chronic intractable pain.

Primary objectives:

1. Pain relief measured using a Visual Analogue Scale (VAS). The average pain reduction experienced as well as the percentage of subjects with at least a 50% pain reduction will be evaluated.

Secondary Objectives:

[figure not shown]

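### The 60 mm entry threshold and the baseline for pain reduction appear to rest on the same diary mean, so without a control arm regression to the mean adds to the apparent benefit; the protocol should name the qualifying reading and separate the two.

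*Protocol*

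**What the plan says.** - **Entry.** Section 4.2, criterion 5: "Average baseline pain rating of 60 mm on the VAS in the primary region of pain". No inequality sign is given; it is read here as a minimum. Section 7.3 makes it binding: "only subjects meeting all Inclusion criteria and none of the Exclusion criteria will be enrolled".
- **Baseline.** Section 7.3: "Baseline pain scores (VAS) will be evaluated using the average score from a 4 day pain diary completed by subjects before their trial procedure". No other pre-treatment VAS is described.
- **Order of events.** Section 3 has subjects screened, consented and enrolled before baseline is measured. Section 7.3 also puts the baseline assessment after screening and consent, and states that "subjects will provide informed consent with an REC-approved Informed Consent Form prior to any data collection".
- **Primary measures.** Section 2: "The average pain reduction experienced as well as the percentage of subjects with at least a 50% pain reduction will be evaluated".
- **Control.** Section 7.2: "As this is a single-arm study, no randomisation or blinding will occur". Section 3 nevertheless describes the trial as "designed to assess the clinical effects of the commercially available Axium® Neurostimulator System".
- **Partial safeguard.** Exclusion criterion 2 in section 4.3 keeps out subjects whose pain worsened or changed in the preceding month, as judged by the investigator's examination.

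**The concern.** A score used to admit subjects above a cut-off is too high on average as a measure of where the admitted group really stands. Candidates whose diary fell in a bad spell pass, and some whose diary fell in a good spell do not. If the same score is the starting point for change, the group mean drifts down at later visits with no treatment effect. A concurrent control would show the same drift and cancel it. Here there is none, so the drift enters the mean reduction and, less directly, the 50% responder share. A confidence interval does not reveal it.

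There is also a problem of wording. Criterion 5 depends on a baseline rating, yet baseline is scheduled after the enrolment decision. A site cannot tell from the protocol which reading settles eligibility.

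**Working it through.** **No figure to reproduce.** The visible protocol gives no SD, correlation, effect size or sample-size derivation, and section 9 is blacked out. The threshold (60 mm) and the maximum N (125, Summary) come from the protocol. All other inputs are assumptions.

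**Assumptions.** Diary means of unselected candidates are normal with mean μ = 65–75 mm and SD σ = 12–18 mm. The correlation between the diary mean and a later score is ρ = 0.6–0.8. Follow-up has the same variance, there is no device effect, and entry requires a diary mean of at least 60 mm. Further selection by the trial-stimulation phase is ignored.

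**Formula.** With a = (60 − μ)/σ and λ = φ(a)/(1 − Φ(a)), the expected fall in the admitted group is σ(1 − ρ)λ.

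| μ | σ | ρ | a | λ | Expected fall |
|---|---|---|---|---|---|
| 75 | 12 | 0.8 | −1.250 | 0.204 | 12 × 0.2 × 0.204 = 0.5 mm |
| 70 | 18 | 0.7 | −0.556 | 0.481 | 18 × 0.3 × 0.481 = 2.6 mm |
| 65 | 18 | 0.6 | −0.278 | 0.630 | 18 × 0.4 × 0.630 = 4.5 mm |

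The first and last rows are the ends of the range. A wider grid (μ 55–75, σ 12–20, ρ 0.5–0.9) gives 0.2 to 9.6 mm.

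**Scale.** If the SD of change is 15–30 mm (assumed) and all 125 subjects contribute, the 95% half-width for the mean change runs from 1.96 × 15/√125 = 2.6 mm to 1.96 × 30/√125 = 5.3 mm. The bias can be as large as the sampling error.

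**Responder share.** In simulation (2,000,000 draws, scores clipped to 0–100, μ 60–75, σ 15–20, ρ 0.5–0.9), regression alone produced 0% to 4.1% responders at the 50% level. If the true reduction were 40%, using the qualifying value as baseline raised the responder share by 0.7 to 9.4 percentage points. At μ 70, σ 15, ρ 0.7 it was 23.9% against 20.7%, a difference of 3.2 points.

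**Which subjects.** For a subject with baseline b, the expected fall is (1 − ρ)(b − μ). At μ = 70 and ρ = 0.7, b = 62 gives 0.3 × (62 − 70) = −2.4 mm, a rise; b = 85 gives 0.3 × 15 = 4.5 mm, a fall. The bias is a property of the group average and grows with baseline.

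**What separating the readings achieves.** If entry uses a screening reading S with the same variance and reliability, and change is measured from diary D to follow-up Y, the expected fall is σ × [corr(S, D) − corr(S, Y)] × λ. Take μ 70, σ 18 and ρ 0.7, so that corr(S, Y) = 0.7.

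- Half the error variance shared by screening and diary: corr(S, D) = 0.7 + 0.5 × 0.3 = 0.85, and the fall is 18 × 0.15 × 0.481 = 1.3 mm.
- All of it shared: corr(S, D) = 1, and the full 2.6 mm remains.
- None shared: the bracket is zero and so is the bias.

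**The case against.** **The single-value premise is an inference.** Sections 3 and 7.3 put baseline after screening, and criterion 5 could mean a rating of average pain rather than an average of ratings. This stands: a reader might take it as settled that the diary decides eligibility, and the documents do not say so outright. But criterion 5 uses both the word for baseline and the word for average, and no other reading is described. If another one is intended, the protocol must name it, which calls for the same edit.

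**The effect is reduced by design.** Averaging four days removes some day-to-day noise, and exclusion criterion 2 targets recent flares. Both lessen the bias. Neither removes it: four consecutive days cannot average out slower fluctuation, and the exclusion rests on clinical examination.

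**Attribution and correction may be dealt with elsewhere.** The Summary and section 1.4 describe post-market data collection, section 9 is blacked out, and the Appendix A table is not shown. A later correction cannot be ruled out. The entry rule and the baseline definition are protocol matters, however, and the visible text provides for neither an unselected mean nor a reliability estimate with which to correct afterwards.

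**Readings that go too far.** A reader might infer that subjects admitted just above 60 mm are the most biased. With a candidate mean of 65–75 mm they are expected to rise. A reader might also infer that a separate screening score removes the bias completely. That requires independent errors, and two readings taken close together may fall in the same spell.

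**Conclusion.** The point holds as a design weakness worth correcting. The direction on group average follows from the entry rule, the baseline definition and the absence of a control, provided that the diary mean is the qualifying value, the threshold excludes some candidates, and the diary is imperfectly correlated with later scores. The size rests wholly on assumed inputs: about 0.5 to 4.5 mm for a candidate mean of 65–75 mm, SD 12–18 mm and correlation 0.6–0.8. It would be smaller if most candidates score well above 60 mm or the diary mean is very reliable.

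It might be inferred that regression could account for the device's whole apparent benefit. The calculation does not support that: a few millimetres would explain only part of a large reduction, and regression alone creates few 50% responders. The mean reduction is affected more directly than the responder share.

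The conflict over which reading decides eligibility needs resolving whatever the size of the bias.

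**What to change.** In sections 4.2 and 7.3:

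1. State that the threshold, written as at least 60 mm if that is the intention, is judged on a separate VAS of average pain in the primary region, recorded at the screening visit after consent.
2. State the interval between that reading and the start of the diary. The longer it is, the less error the two readings are likely to share.
3. Use the 4-day diary mean only as the baseline for the two primary measures.
4. State that a subject who qualified at screening is not excluded afterwards because the diary mean is below 60 mm.

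Section 3 should describe the same order of events.

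The cost is one extra VAS item, the wording changes, and whatever scheduling the interval needs. Some diary baselines will lie below 60 mm, and the reported reduction will be slightly smaller. The change reduces the bias but does not guarantee its removal (1.3 mm of 2.6 mm remains in the half-shared case), so the report should still not attribute all of the change from baseline to the device.
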